5.8 Informed Consent Procedures

5.8A. Veteran Informed Consent.

After completing the recruitment steps described above, Veterans will participate in informed consent procedures. Veteran participants will participate in informed consent over the telephone with a study staff member. Subjects can meet with a study staff member for in-person informed consent if they prefer.

Veteran participants will receive all of the information contained within informed consent by mail or electronically through Docusign. The mailing will contain an opt-out option for those who do not want to be contacted any further along with 1) information explaining the risks and benefits of study participation, 2) their rights as study participants and their privacy rights and 3) required elements of informed consent 4) HIPAA authorization. This material will then be reviewed by telephone prior to participation. When the telephone consent is obtained, they will have already had the opportunity to review study details, consider their participation, and consult with loved ones about participation. Discussing this material with a staff member over the phone will provide greater time and freedom to consider or decline study participation, prior to investing more time and energy in the study. Staff will solicit and answer all questions, and they will also ask the participants questions to ensure participant comprehension of the informed consent document including, but not limited to, what their understanding is of the risks and benefits of participation, when assessments will occur and what topics they will cover. The team is sensitive to the importance of the informed consent process and will make every effort to ensure that participants give their consent voluntarily and fully informed about the potential risks and benefits. If a participant agrees to participate in the study, an informed consent form and HIPAA authorization form will be signed by hand or electronically via Docusign by the participant. If signed by hand, the participant will mail the form back to study staff. All signed forms will be kept locked in staff file cabinets in a locked office. When signed electronically using Docusign, staff can access the signed form in the online Docusign sharepoint space and will export the document to study files.

If a participant requests to have an informed consent meeting face-to-face with a study staff member, this will be permitted. Some participants may prefer to coincide other appointments at the VA with an in-person consent meeting with our study staff. Participants meeting in-person for informed consent will also be required to sign an official informed consent form, and a HIPAA authorization form.

Informed consent will be obtained before obtaining any Baseline self-reports or Baseline clinical interviews. As these Baseline procedures are also necessary for establishing final eligibility (SCID-5-CT and CAPS-5; IC: PCL-5, PHQ-9, AUDIT, DAST), Veterans will be notified that the baseline procedures are necessary for establishing final eligibility and they may be deemed ineligible for the study after these procedures. They will receive notification of their edibility and contacted by staff to schedule their first therapy appointment. Individuals deemed ineligible will be told by telephone and Veterans referred back to their referring providers.

When Veterans are deemed ineligible by a study assessor after completion of the Structured Clinical Interview (i.e., positive screens for psychosis, substance use, suicidality, homicidally, etc.), study staff will communicate the assessment results of these ineligible subjects back to the treatment team (non-study clinical staff) for purposes of patient treatment planning and continuity of care. Conveying a patient's assessment results to the treatment team allows patients to be referred to appropriate treatment in a timely manner, while also eliminating any inconvenient and redundant reassessments. This will be proposed to participants during informed consent, and patients will have the ability to decline this request

5.8B. LO Informed Consent

Loved ones will be sent a letter and brochure describing the study, an informed consent form, and a HIPAA authorization form. The letter will inform them that they will be contacted and how to decline study recruitment efforts. They will then be contacted by telephone by a trained interviewer to discuss the study, their interest, and assess the presence of severe relationship violence. The study procedures (assessment data gathering, intervention, audio/videotaping) will be fully described to the participant at the time of the initial phone call. Participants will be informed of the study design (including randomization to condition) before they decide to participate. If the participant agrees to take part in the study, they will sign the informed consent form and HIPAA authorization by hand or electronically via Docusign. If signed by hand, the participant will mail the form back to study staff. All signed forms will be kept locked in staff file cabinets in a locked office. When signed electronically using Docusign, staff can access the signed form in the online Docusign sharepoint space and will export the document to study files.

If Veterans are deemed ineligible due to inclusion/exclusion criteria or lack of interest, LOs will be informed that full inclusion/exclusion criteria were not met for the Veteran and thus the dyad is no longer eligible for enrollment. Specific details on which inclusion/exclusion criteria (including level of interest in the study) will not be disclosed. The same approach will be used for LOs who decline participation or report severe relationship aggression (i.e., Veterans will be informed that full inclusion/exclusion criteria were not met for the Veteran and thus the dyad is no longer eligible for enrollment). Appropriate alternative referrals to mental health treatment, including substance use treatment or psychotherapy, or to address relationship aggression will be made as upon request and when clinically indicated (i.e., positive screens for psychosis, substance use, suicidality, homicidally, etc.).

5.8C. Retaking Baseline Assessments

For safety and risk implications, we will require Veteran and SP participants to retake the baseline survey and preclinical assessment if the therapy start date would occur 2 months after their baseline data was collected. Time gaps between baseline data and therapy start dates can occur for various reasons, including scheduling issues, provider availability, patient travel arrangements, etc. It is important that patient baseline data is as close to therapy start dates as possible, as clinical data can change over several weeks. For example, in the gap between assessment and therapy start, patients could have a serious substance use relapse or a suicide attempt that would then make it clinically inappropriate for them to begin a trauma-focused therapy, prior to addressing their more pressing concerns around establishing their safety or sobriety. Additionally, we expect many of the constructs we assess to naturally change with time (e.g., family functioning, relationship satisfaction). So, baseline assessments that are more than 2 months old at the time of therapy start may no longer truly represent the patient, support person, or family functioning at the beginning of treatment, confounding study results.

Subjects will be informed of this requirement during the informed consent process and on the information packet or informed consent form. Participants would get paid again for retaking these assessments (\$50 for the baseline survey; \$60 for the preclinical interview).

5.8D. Incentives.

Participants will receive \$40 for participating in Baseline surveys, \$50 for baseline diagnostic interviews (Veterans only), \$60 for posttreatment surveys, \$60 for posttreatment diagnostic interviews (Veterans only), and \$60 for one-time qualitative exit interviews. Both veterans and intimate partners will complete monthly surveys for outcomes and treatment mechanisms. They will receive \$25 for each of these surveys. Additionally, participants receive \$70 for completing a 3-month follow-up survey. A possible total of \$415 for veterans and \$305 for loved ones.

Participants will receive payment by direct deposit or debit card after completion of their baseline assessment and interview, post treatment assessment and interview, and exit interview.

5.9 Inclusion/Exclusion Criteria

See Table X. With the exception of criteria relevant to LO inclusion (criteria 3, 4, 10, & 11), inclusion/exclusion criteria reflect those consistent with PE delivery within VA. Participants must meet diagnostic criteria for PTSD,⁹¹ assessed using the gold-standard Clinician-Administered PTSD Scale for DSM-5 (CAPS-5; Item 2).³ Structured clinical interview for inclusion/exclusion criteria will be administered by trained and supervised assessors (Items 10, 11, 12).

Table x. Inclusion/exclusion criteria

Inclusions	Measure	Exclusions	Measure
1. Male or female Veterans at least 18 years old. Enrolled in VHA care.	CPRS	9. Recent suicidal or homicidal ideation with intent SCID-5-CT ¹² and/or plan that, in the judgment of the investigator, should be the focus of treatment	

2. Participant meets full DSM-5 diagnostic criteria for PTSD.		10. Hospitalized or meets DSM-5 criteria for a manic, hypomanic, or psychotic episode in the past 3 months	SCID-5-CT ¹²
3. Has an intimate partner with whom they've been in a committed relationship with for the last 6 months and have some form of contact with at least 5 days a week.	Self-report item	11. Meets DSM-5 diagnostic criteria for a severe substance use disorder in the past 3 months. Of note, subjects can be abusing or dependent upon nicotine or marijuana and still be included in the study	SCID-5-CT ¹²
4. Interested in participating weekly psychotherapy for PTSD with this person.	Self-report item	12. Moderate relationship violence between the identified partner and the Veteran, defined as one or more episodes of severe violence in the past year (e.g., punched, kicked, or beat up).	IPSVS Adapted ¹⁰⁸
5. Provides informed consent.	Self-report item	13. Partner screens positive for PTSD on a self-report instrument (PCL).	PCL-5
6. Speaks and reads English.	Self-report item	14. Having an ongoing medical condition that would interfere with ability to attend weekly treatment sessions.	Self-report item
7. Willing to have their therapy sessions recorded.	Self-report item	15. Having any planned upcoming major medical procedure or personal event over the next several months that would prevent them from attending weekly treatment sessions.	Self-report item
8. Willing and able to be seen via telehealth when in-person treatment options aren't available.	Self-report item	16. Severe cognitive impairment	CPRS
		17. Fails to complete baseline survey.	

Relationship violence will be assessed by telephone from both Veteran and LO-report (Item 13). We will exclude Veteran participants if he/she has an underlying medical condition or a medical procedure (item 15 and 16) planned that would greatly impair their ability to participate in a weekly psychotherapy (i.e., a severe seizure disorder making weekly attendance difficult or a planned major surgery within a month of beginning treatment). This item will be assessed during the initial phone screening. Items 3, 4, 8, and 14 will also be assessed by phone screen. See materials document for screening items. We will administer a PTSD screen including the PCL-5, PHQ9, and questions regarding prior hospitalizations for MH concern, by telephone. If the loved one has (1) a PCL score above a 32, (2) a PHQ9 score of 9 or 10, and (3) they have ever had a hospitalization for MH or SUD concerns, a further case review will be conducted by a psychologist on the team. LOs and Veterans will be required to complete a baseline survey assessment before they can be randomized to a study arm. Failure to complete the baseline survey will result in study ineligibility (item 18).

We will exclude dyads in which either the Veteran or LO report moderate relationship violence (item 12), defined as one or more episodes of severe violence in the past year (e.g., kicked or beat up) on the IPSVS Adapted Scale¹⁰⁶. It would be counter-indicated for providers to proceed with PTSD treatment, without addressing ongoing significant relationship violence first. This is similar to the requirement that the patient must not be actively psychotic, manic, suicidal, or dependent on substances. Consequently, the reporting dyad member(s) will be provided with resources and referrals for IPV (see IPV risk algorithm). The dyad may be re-evaluated for eligibility when this exclusionary criteria has been resolved (i.e., one year has passed without an episode of severe violence). Finally, we can delay or end treatment, when clinically indicated, based on case review. For example, if the veteran is new to mental health care at the Minneapolis VA and

has a history of suicidal ideation, the team can elect to delay entry into the study until the patient has established mental health care with the Minneapolis VA (e.g., assignment of an mental health treatment coordinator and a treatment plan) to determine if the patient needs a higher level of treatment than is provided by the limited services in the study before proceeding.

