Our overall goal is to develop and pilot a couple-therapy approach to Prolonged Exposure that integrates loved ones into every session of PE. We will combine techniques from Integrative Behavioral Couples Therapy and a brief, three-session approach to involving family in PE (Partner Enhanced Prolonged Exposure). We anticipate this intervention will teach couples to embrace a lifestyle that supports confronting trauma-related distress, so the veteran can achieve optimal functional recovery, while improving both social and family functioning. We will complete stages 1A and 1B of the Stage Model of Treatment Development.²⁵ This includes the following aims:

Aim 1: Expand our treatment outline using content experts and feedback from key **stakeholders** (veterans, loved ones, providers, and VA mental health leadership).

Aim 2: Conduct a pilot **open trial** to assess (a) the acceptability of treatment components, structure, and materials, (b) the feasibility of the intervention (retention and intervention fidelity), and (c) the study approach (screening, recruitment, and assessment process).

Aim 3: Explore the preliminary effects of the intervention on select outcomes including overall functioning, mental health functioning, social functioning, family functioning, and potential mechanisms (social control, subjective norms, and the degree to which veterans rely on their partners for support).

Impact: PTSD treatments (including PE and CPT) have been criticized for a narrow focus on symptom gains over goals that may be more meaningful to veterans, such as greater quality of life, interpersonal connections, and social functioning.^{26,27} Our proposal aims to expand the explicit targets of PE to these patient-centered outcomes. If our approach to a couple-based exposure therapy demonstrates promise, this proposal could provide the first step in a series of studies that **feed the evolution of one-on-one symptom-focused psychotherapies into family-based interventions designed to lift the whole household**. Our approaches could inform adaptations to interventions for a myriad of problems including suicide prevention, TBI rehabilitation, and pain management, contributing to a broader evolution towards evidence-based, family-inclusive care focused on outcomes with meaning to veterans.

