This study involves minimal risk. COACH is a flexible length cognitive-behavioral, loved one-assisted, treatment for PTSD that draws from PE, ICBT, and PE². Treatment is typically between 13 and 15 sessions, but can be fewer or more based on patient need and symptom response. There are no anticipated physical risks in this study. Economic risks include potential loss of wages when traveling to and participating in the research intervention. The questionnaires ask questions consistent with those included in routine clinical care, and participants can refuse to answer any question(s). Individuals may experience some psychological or social discomfort during the course of the study; however, the intervention is likely to increase their well-being. Additionally, the risks are no greater than those encountered in routine clinical care.

5.6B. Protection Against Risk

B.1. Social and Psychological

Appropriate safeguards will be in place if screening interviews, assessments, interviews, or therapy sessions cause any psychological distress, a psychiatric emergency emerges among participants, or severe interpersonal violence (SIV) is reported. Severe violence will be defined as one or more episodes of severe violence in the past year (e.g., beating up, threatening with a knife or gun). The PI has expertise in assessing and managing risk for SIV, including within a clinical trial, and will closely train and supervise study staff in assessing and managing risk for SIV.

All surveys will be screened upon receipt by study staff. If a psychiatric emergency is reported on surveys (i.e., expression of risk for suicide or homicide), veterans MH providers will be notified. MH providers will follow-up as they deem clinically indicated. If the participant does not

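### The PHQ-9 condition for loved-one case review in section 5.9 stops at 10, so the rule as written passes over higher depression scores whether its conditions are joined by *and* or by *or*

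*Combined protocol and SAP*

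**What the plan says.** Section 5.9 (Inclusion/Exclusion Criteria) describes a telephone screen: "We will administer a PTSD screen including the PCL-5, PHQ9, and questions regarding prior hospitalizations for MH concern, by telephone". One sentence then sets out when a loved one goes to case review by a psychologist on the team. It has three conditions:

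- PTSD symptoms: "If the loved one has (1) a PCL score above a 32";
- depression: "2) a PHQ9 score of 9 or 10";
- history: "and (3) they have ever had a hospitalization for MH or SUD concerns, a further case review will be conducted".

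In the same section, Table x, item 13 excludes the dyad on a related ground: "Partner screens positive for PTSD on a self-report instrument (PCL", measured by the PCL-5. No cut-off is given there. Table x has no criterion for depression in the partner.

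Section 5.9 also keeps a general discretion: "Finally, we can delay or end treatment, when clinically indicated, based on case review". Section 5.6B adds a check on incoming surveys: "If a psychiatric emergency is reported on surveys (i.e., expression of risk for suicide or homicide), veterans MH providers will be notified". If there is no provider, or the provider cannot be reached, the principal investigator or a co-investigator telephones the participant.

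**The concern.** A severity trigger should not switch off as severity rises. In this sentence the PCL condition has a lower limit and no upper one. The PHQ-9 condition names two adjacent values and says nothing about higher scores. A loved one at 9 or 10 meets it, and one at 20 does not.

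This matters because of the loved one's role. Section 3.0 describes a treatment that "integrates loved ones into every session of PE", and sessions in the active phase include imaginal exposure (section 5.2A). By giving loved ones the PHQ-9 at screening and tying review to the result, the team showed that it considers their depression worth checking before entry. Taken literally, the check misses the higher scores. Screening is also one of the feasibility questions under Aim 2, so a faulty rule could be carried into the later randomized trial.

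**Working it through.** The plan has no figure to reproduce, so the check is to apply the rule to every score combination.

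**Inputs.** From section 5.9: PCL above 32; PHQ-9 equal to 9 or 10; any past mental-health or substance-use hospitalization (H); joined by *and*. Assumed, because the documents give no ranges: PHQ-9 from 0 to 27 and PCL-5 from 0 to 80. The direction of the result needs only that PHQ-9 scores above 10 exist.

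**Counts.** Possible PHQ-9 values: 27 − 0 + 1 = 28. Values in the band: 2. Values above it: 27 − 10 = 17.

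**The rule under each connective.**

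- *And*, as written: review = (PCL > 32) and (PHQ-9 is 9 or 10) and H.
- *Or*, a possible intended reading: review = (PCL > 32) or (PHQ-9 is 9 or 10) or H.

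| Loved one | *And* | *Or* |
|---|---|---|
| PHQ-9 values at which review is possible at all | 9 and 10 only | all 28 |
| PCL ≤ 32, no hospitalization: values reviewed | none | 9 and 10 only |
| PCL ≤ 32, no hospitalization: values 11–27 not reviewed | 17 of 17 | 17 of 17 |
| PCL ≤ 32, past hospitalization: values 11–27 not reviewed | 17 of 17 | 0 of 17 |

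Under *and*, no score from 11 to 27 leads to review, whatever the PCL score or history. Under *or*, a high scorer is reviewed only through the PCL or the hospitalization history.

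**Would a single edit be enough?** No.

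- Remove the upper end of the band but keep *and*: a loved one with PHQ-9 of 27, PCL of 20 and no hospitalization fails two conditions and is not reviewed.
- Change *and* to *or* but keep the band: a loved one with PHQ-9 of 20, PCL of 20 and no hospitalization meets no condition and is not reviewed.

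**Does another stated rule send these loved ones to review?**

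- Table x, item 13 concerns PTSD only.
- Section 5.3A lists the partner-side conditions for continuing as agreement to take part, no reported partner violence and a negative PTSD screen.
- The loved-one call in section 5.8B covers interest and relationship violence.
- Items 9 to 11 rest on the SCID-5-CT, and Table A in section 5.6 lists a structured interview for veterans only.
- Survey screening in section 5.6B acts on suicide or homicide risk, not on a depression score.
- The discretion to delay or end treatment in section 5.9 itself depends on case review, and its example concerns a veteran.

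**Overlap with item 13.** Under *and*, review requires a PCL above 32. If 32 is also the item 13 cut-off (an assumption; none is stated), everyone who qualifies for review is already excluded, and the two provisions conflict.

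**The case against.** The strongest reply is that the wording is shorthand or a slip for an open-ended cut-off, and that trained staff would not pass over a high score. The screening items are in a separate materials document that is not available here, so what screeners actually do cannot be established. That stands as a limit on the safety inference. It does not alter the protocol text, which is the rule on record.

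Three stronger readings are tempting, and the documents do not support them.

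- A reader might infer that review turns on the PHQ-9 alone. It does not: the PHQ-9 is one of three conditions. As written, a score of 9 or 10 is necessary but not sufficient.
- A reader might infer that the most depressed loved ones always enter unreviewed. Under *or*, those with a PCL above 32 or a past hospitalization are reviewed. Under either reading, a loved one who screens positive for PTSD is excluded by item 13. A loved one with a PCL of 40, a past hospitalization and a PHQ-9 of 20 may therefore never enter.
- A reader might infer that nothing else monitors loved ones' mood. Table 1 lists the PHQ-9 within a mental-health domain reported by loved ones as well as veterans, Table A includes symptom surveys for them during treatment, surveys are screened for emergencies, and therapists see them weekly. None of these is a stated route from depression severity to case review, so the narrower point survives.

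**Conclusion.** The point holds as a wrong decision threshold in one sentence of section 5.9. Under *and*, no loved one with a PHQ-9 above 10 can be sent to review by this rule. Under *or*, the gap is confined to those with a PCL of 32 or less and no past hospitalization. Under both, some loved ones above 10 are neither reviewed nor excluded under Table x. Unreviewed here means not reviewed under this sentence; the emergency and discretionary safeguards remain.

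The count of 17 of 28 rests on the assumed 0 to 27 range and counts score values, not people. It does not estimate how many loved ones would be affected, and in an open trial of 12 veterans and their loved ones (section 5.1) the number is likely to be small. Confidence is high on the wording and lower on what happens in practice. The correction is worth making because the rule works against its evident purpose and is cheap to put right.

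**What to change.** Revise the case-review sentence in section 5.9 as a whole, in four parts:

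1. State the intended PHQ-9 range so that higher scores are not passed over when lower ones are reviewed. The threshold is the sponsor's clinical decision, and none is proposed here.
2. State whether the three conditions are joined by *and* or by *or*, and check that the choice lets a high PHQ-9 score reach review as the sponsor intends. Changing the band alone, or the connective alone, leaves the gap open.
3. Reconcile the PCL condition with Table x, item 13: give the cut-off for a positive partner screen, and say which loved ones are excluded outright and which go to review.
4. Make the telephone screening script match.

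The cost is a one-sentence edit with matching changes to item 13 and the script, and possibly a few more case reviews by a psychologist already on the team.
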